Official title Clinical Characteristics and Outcomes Until 2 Years of Age in Preterm Infants With Typical Chest Imaging Findings of Bronchopulmonary Dysplasia: A Propensity Score Analysis

NCT number 04163822

Document date 2021.5.18

Bronchopulmonary dysplasia (BPD) is a common chronic respiratory disease in preterm infants. The increase in the survival rate of premature babies following the improvement of perinatal treatment and care has caused an increase in the incidence of BPD in recent years, which has seriously affected the quality of life of preterm infants. According to the consensus reached at the workshop sponsored by the National Institute of Child Health and Human Development (NICHD) in 2001, BPD was clinically defined based on oxygen dependency in preterm infants. However, the refined NICHD definition of BPD in 2018 emphasized imaging findings to support a diagnosis of lung parenchyma disease.

Fibrotic opacities and cystic changes on chest imaging [chest X-ray (CXR) or computed tomography (CT) scan] were considered typical findings in BPD patients. In patients with severe BPD, the presence of bubbles/cystic appearance on CXR after 28 days of life was reported to be an important factor, and typical imaging findings can predict a poor pulmonary outcome in BPD patients. BPD is associated with poor outcomes. Although many studies have been conducted on BPD, there are limited reports specifically evaluating the association of typical imaging findings with clinical characteristics and later outcomes in patients with BPD.

We hypothesized that BPD with typical imaging findings was likely to be a particular subgroup of this entity, with a unique etiology, clinical characteristics and prognosis. Therefore, we performed a retrospective cohort study using data from the Department of Neonatology, Children's Hospital of Chongqing Medical University (CHCMU), and the patients were followed by telephone. Eligible patients fulfilled the following three criteria simultaneously: (1) BPD diagnosis according to the 2001 NICHD consensus; (2) chest imaging examination (CXR or CT) in the first week after birth; and (3) hospitalization within the first 7 days after birth. Patients were excluded from the study if they met one of the following conditions: (1) major congenital malformations or laboratory-confirmed chromosomal abnormalities; (2) inadequate clinical data or missing chest imaging data; or (3) loss to follow-up.

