Relevant data were retrospectively collected, including demographics [i.e., sex, gestational age, age at admission, birth weight (BW)], perinatal factors [i.e., pregnancy induced hypertension (PIH), CAM, cesarean section, prenatal glucocorticoid administration, respiratory distress syndrome (RDS), sepsis, PDA, 5-min Apgar score], management during hospitalization [i.e., surfactant administration, noninvasive and invasive mechanical ventilation (IMV), postnatal

glucocorticoid administration, packed red blood cell (PRBC) transfusion], complications during hospitalization [i.e., IVH, retinopathy of prematurity (ROP), NEC], and outcomes. Primary outcomes were the severity of BPD, HOT at discharge, and mortality between 28 days after birth and 2 years of age. Secondary outcomes were (1) duration of hospital stay; (2) duration of oxygen supplementation; (3) routine physical assessment; (4) wheezing disorders; and (5) clinical visits and rehospitalizations for a respiratory reason between discharge and follow-up. The long-term outcomes were evaluated until 2 years of age.

Statistical Analysis

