Statistical analysis was performed using SPSS 26.0. We used the Shapiro-Wilk test to analyze the normality of the data distribution. Variables without normal distributions were analyzed using the Wilcoxon-Mann-Whitney test and are reported as medians [interquartile ranges (IQRs)]. All normally distributed variables were analyzed using a t-test for comparisons of two independent groups and are presented as the means \pm standard deviations. Categorical variables were analyzed using the chi-square test or Fisher's exact tests and are reported as the numbers (%) of subjects. To further evaluate the associations between typical chest imaging findings and the primary and secondary outcomes, a propensity score analysis with 1:1 matching was performed. The following covariates were included based on previous studies: GA, BW, cesarean section, CAM, PIH, sepsis, RDS, PDA, prenatal glucocorticoid administration, postnatal glucocorticoid administration, NEC, IVH, RSD, IMV \geq 7 days, \geq 2 PRBC transfusions. The nearest neighbor matching method was used to select each matched pair by using calipers with a width equal to 0.01 of the standard deviation of the logit of the propensity score. Typical chest imaging findings and the above 15 covariates were analyzed for collinearity and incorporated into the multivariate binary regression model, and the forward likelihood ratio (LR) was used to select the variables to further determine the independent factors of BPD infant mortality. A p-value < 0.05 was considered statistically significant.

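### Siblings from multiple births are neither excluded nor identified, and every named test assumes independent infants, so p-values are modestly miscalibrated if siblings are enrolled

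*Combined protocol and SAP*

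**What the plan says.** The opening section sets three inclusion criteria: BPD by the 2001 consensus, chest imaging in the first week, and hospitalization within the first 7 days. It also sets three exclusions: "major congenital malformations or laboratory-confirmed chromosomal abnormalities"; inadequate clinical data or missing imaging; and loss to follow-up. Neither list mentions multiple birth or a limit of one infant per mother.

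The data-collection paragraph lists sex, gestational age, age at admission and birth weight as demographics. It then lists "perinatal factors [i.e., pregnancy induced hypertension (PIH), CAM, cesarean section, prenatal glucocorticoid administration", followed by RDS, sepsis, PDA and the 5-minute Apgar score. No multiple-birth flag or family identifier appears there or among the 15 matching covariates.

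The Statistical Analysis section names these methods:

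- normally distributed variables are tested with a t-test, for "comparisons of two independent groups";
- "Variables without normal distributions were analyzed using the Wilcoxon-Mann-Whitney test";
- "Categorical variables were analyzed using the chi-square test or Fisher's exact tests";
- for mortality, imaging findings and the covariates are "incorporated into the multivariate binary regression model, and the forward likelihood ratio (LR) was used to select the variables".

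It also plans 1:1 propensity score matching but names no separate test for the matched set. The decision rule is: "A p-value < 0.05 was considered statistically significant". No mixed model, GEE, cluster-robust variance or one-infant-per-family analysis is named.

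**The concern.** This is a single-department cohort of preterm infants with no restriction on plurality, so two siblings who both develop BPD can both qualify. They would normally share the pregnancy-level factors that the plan itself collects (hypertension, CAM, prenatal glucocorticoids) and often gestational age. After discharge they would usually share a household. Because follow-up is by telephone, one caregiver may also report wheezing, visits and rehospitalizations for both.

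Adjusting for measured covariates does not remove a shared household or a shared informant. Matching does not deal with it either, because it balances covariates between imaging groups and leaves correlation within families in place. Forward likelihood-ratio selection is exposed in the same way: it uses a likelihood that treats infants as independent to decide which mortality factors are kept.

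What is at stake is the calibration of p-values near the 0.05 threshold. Shared household and reporting bear most directly on the respiratory outcomes after discharge, which are secondary.

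**Working it through.** The documents give no sample size, sibling count or correlation, so there is no figure of the plan's own to reproduce. The check shows the direction and plausible size of the error under stated assumptions.

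**Inputs**

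- Nominal level 0.05, from the Statistical Analysis section. Two-sided is assumed because sidedness is not stated; critical value 1.96.
- t, the share of infants with a sibling in the cohort: assumed 0.1-0.3.
- rho, the correlation of the outcome between siblings: assumed 0.1-0.5.
- c, the share of sibling pairs with both infants in the same imaging group: unknown, varied from 1 to 0.

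**Formula.** Take two equal groups of n infants with outcome variance s². Under independence, the difference in means has variance 2s²/n. There are t × n sibling pairs. Each concordant pair adds 2 × rho × s²/n² to that variance, and each split pair subtracts the same amount. Hence

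true variance / independence variance = 1 + rho × t × (2c − 1)

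actual alpha = 2 × (1 − Phi(1.96 / sqrt(ratio)))

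**Results**

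| t | rho | c | Variance ratio | True SE / assumed SE | Actual alpha |
|---|---|---|---|---|---|
| 0.1 | 0.1 | 1 | 1.010 | 1.005 | 0.0511 |
| 0.3 | 0.5 | 1 | 1.150 | 1.072 | 0.0676 |
| 0.3 | 0.5 | 0.75 | 1.075 | 1.037 | 0.0587 |
| 0.3 | 0.5 | 0.5 | 1.000 | 1.000 | 0.0500 |
| 0.3 | 0.5 | 0 | 0.850 | 0.922 | 0.0335 |

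For the second row, 1 + 0.5 × 0.3 = 1.15, sqrt(1.15) = 1.072 and 1.96/1.072 = 1.828, which gives alpha 0.0676. Over the assumed ranges with all pairs concordant, the standard error is understated by 1 − 1/1.005 = 0.5% up to 1 − 1/1.072 = 6.7%.

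**Simulation.** With t-tests, 100 infants per group (assumed) and 20,000 replicates at t = 0.3 and rho = 0.5, the rejection rate was 0.070 with all pairs concordant, 0.052 with about half concordant, and 0.034 with all pairs split. These agree with the formula.

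**Wider inputs.** At t = 0.4 and rho = 0.8, alpha is 0.088 with all pairs concordant (ratio 1.32) and 0.0175 with all pairs split (ratio 0.68).

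The formula is for equal groups and a difference in means. With unequal imaging groups the break-even concordance need not be exactly 50%. For the rank, exact and likelihood-ratio tests the figures are a guide to size only.

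**The case against.** The strongest reply is that the documents show no actual defect in the data. They never mention siblings. To count, both siblings must have BPD, reach this department within 7 days, be imaged in the first week, have adequate records and be followed up. In the matched analysis both must also find a partner within a caliper of 0.01 standard deviations of the logit. The share and the correlation used above are assumptions, and even their upper end moves a 5% test only to 6.8%. Pairs split between the groups pull the other way. All of this stands, and it limits the point to a minor one.

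Several stronger readings are tempting and should be resisted:

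- **That the plan's standard errors are too small.** This holds only where siblings mostly share an imaging group. The documents say nothing about concordance, so the net direction is undetermined.
- **That the phrase about two independent groups claims independence of infants within a group.** It describes an unpaired test between groups. The point rests on the full list of methods and the absence of any family-level one.
- **That every analysis is affected.** This can be said only of the tests named; the test for the matched set is not stated.
- **That confidence intervals are too narrow.** The plan names no intervals, so the effect falls on p-values.
- **That plurality was not collected.** The variable list is introduced as a list of what was included, so absence from it shows only that plurality is undocumented.

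The reply does not remove the gap itself: as documented, the plan gives no way to tell whether siblings are present, and no method for handling them if they are.

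**Conclusion.** The point holds as a conditional one of modest size. Siblings are not excluded, no identifier is documented, and every named test treats infants as independent. If siblings are enrolled and their outcomes are positively correlated, p-values are too small when pairs are mostly concordant, too large when they are mostly split, and about right at 50% concordance with equal groups.

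Under the assumed shares and correlations, alpha stays between 0.051 and 0.068 even if every pair is concordant. Errors of this size could change a borderline p-value but are unlikely to overturn a clear result. This is a worthwhile refinement, not a threat to the study's conclusions.

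**What to change.** 1. Take the mother identifier from the existing charts and report the number of sibling sets by imaging group, separating concordant from split sets. If there are none, one sentence closes the matter.
2. If there are any, repeat the primary outcome comparisons and the mortality model with one randomly chosen infant per mother. Redo the propensity matching in that set, since dropping a sibling breaks existing pairs, and rerun the forward selection instead of refitting the variables already chosen.
3. Where a regression model is used, give GEE or cluster-robust standard errors by mother. This does not carry over to the Wilcoxon-Mann-Whitney and Fisher's exact tests, and it does not repair the forward selection step. The one-infant-per-mother repeat is therefore the main check.

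The cost is one identifier from records already held, some extra analysis, and a smaller sample in the repeat. If all sibling sets are pairs, dropping one of each removes t/2 of the infants: 0.1/2 = 5% to 0.3/2 = 15% over the assumed range. The main analysis keeps all infants.

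### Apart from mortality, no outcome has a covariate-adjusted analysis after propensity matching, and no balance check is specified

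*Combined protocol and SAP*

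**What the plan says.** All of this stands in the Statistical Analysis section of the combined protocol and SAP, except the outcome list, which is in the unnumbered text just before it.

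- **Matching.** "a propensity score analysis with 1:1 matching was performed". The score has 15 covariates, GA and BW first: "The following covariates were included based on previous studies: GA, BW, cesarean section, CAM, PIH, sepsis, RDS, PDA", and so on. Pairs are nearest neighbours within "calipers with a width equal to 0.01 of the standard deviation of the logit of the propensity score". Nothing requires the two infants in a pair to be close on GA or BW themselves.
- **Group comparisons.** "Variables without normal distributions were analyzed using the Wilcoxon-Mann-Whitney test". "All normally distributed variables were analyzed using a t-test for comparisons of two independent groups". "Categorical variables were analyzed using the chi-square test or Fisher's exact tests". These are the only tests named for comparing groups, and none takes a covariate. The section does not separately say how the matched set is to be tested.
- **Regression.** "Typical chest imaging findings and the above 15 covariates were analyzed for collinearity and incorporated into the multivariate binary regression model", with forward likelihood-ratio selection. It serves mortality only, and the section does not say whether it is fitted to the full cohort or the matched set.
- **Balance.** No standardised differences or other post-match check is described.
- **Outcomes.** The primary outcomes are BPD severity, HOT at discharge and mortality. Hospital stay and oxygen duration are among the secondary outcomes.

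**The concern.** A shared score is not a shared GA. A very preterm infant with few other risk factors can be paired with a more mature infant who has several. Averaged over many pairs these differences cancel, because GA and BW are in the score. In one small matched set they may not cancel fully, and an unadjusted test attributes whatever difference remains to imaging. If the form in which GA or BW enters the score is wrong (the plan does not state it), imbalance could be systematic, and no planned step would show it.

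The second cost is precision. Where GA and BW predict the outcome, as is plausible for days in hospital and days on oxygen, the unadjusted comparison leaves that variation in the error term. Both variables are already collected and already judged relevant enough to match on, so the information is available and unused at the outcome stage.

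**Working it through.** **No plan figure to reproduce.** The documents give no cohort size, number of pairs, effect size, SD or event rate. Every number below is an illustration under stated assumptions.

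**Step 1. Which outcomes are adjusted?**

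| Outcome | Matched comparison | Covariate model |
|---|---|---|
| BPD severity, HOT (primary) | unadjusted test | none |
| Mortality (primary) | unadjusted test | binary regression; GA and BW are candidates and may be dropped; sample not stated |
| All secondary outcomes | unadjusted test | none |

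**Step 2. Does matching leave a GA difference between groups?** Simulation inputs (assumed): cohorts of 200 or 400, about 33% exposed, 15 covariates (GA and BW correlated 0.7, plus 13 binary), a correctly specified logistic score, greedy 1:1 matching at 0.01 SD of the logit, and 400 replicates per scenario.

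| | about 25 pairs (N=200) | about 73 pairs (N=400) |
|---|---|---|
| Mean within-pair GA gap | about 0.90 SD | about 0.85 SD |
| Mean group GA difference, before matching | about -0.53 SD | about -0.53 SD |
| Mean group GA difference, after matching | about 0 | about 0 |
| SD of that difference across data sets | about 0.18 | about 0.09 |
| Data sets with difference above 0.1 SD | 51–60% | 23–28% |
| Data sets with difference above 0.2 SD | 22–29% | 2–4% |

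Pairs therefore differ in GA while the groups do not differ on average. The largest bias of the unadjusted estimate was 0.024 SD, about two Monte Carlo standard errors (0.247/√400 = 0.012) and the largest of 12 scenarios. Type I error of the independent t-test was 2 to 4.5%.

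What could a chance imbalance do in one data set? If GA alone carried the explained variance R², a GA difference of 0.2 SD would move the outcome by 0.2 × √R²: 0.2 × √0.3 = 0.11 SD, or 0.2 × √0.5 = 0.14 SD.

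**Step 3. Precision, closed form.** Adjustment replaces the outcome SD by SD × √(1 − R²). For an assumed effect of 0.5 SD, two-sided alpha 0.05 and 80% power, n per group = 2(1.96 + 0.842)²/0.5² = 62.8, so 63.

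| R² | Power at 63 per group (unadjusted 80.1%) | n per group for 80% |
|---|---|---|
| 0.1 | 84.1% | 57 |
| 0.3 | 91.8% | 44 |
| 0.5 | 97.8% | 32 |

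**Step 4. Precision after matching.** Same simulation, effect 0.5 SD, independent t-test versus regression on imaging, GA and BW:

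| R² | about 25 pairs | gain (points) | about 73 pairs | gain (points) |
|---|---|---|---|---|
| 0.1 | 47.0% v 48.5% | 1.5 | 85.5% v 87.5% | 2.0 |
| 0.3 | 39.8% v 50.5% | 10.7 | 89.2% v 93.8% | 4.6 |
| 0.5 | 44.0% v 70.3% | 26.3 | 92.0% v 98.8% | 6.8 |

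Part of this gain is not smaller sampling error. At R² = 0.5 with 25 pairs, the empirical standard error fell only from 0.226 to 0.205 (9%). The independent t-test works with roughly √(2/25) = 0.283, because it ignores the balance that matching has already produced. That is also why its type I error is below 5%.

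**Step 5. Other checks.** A second simulation (45% exposed, about 30 or 86 pairs, effect 0.4 SD, regression clustered on pair) gave a 12% lower standard error than a paired t-test at R² = 0.4 and about 4–5% lower at R² = 0.2. Type I error of the adjusted analysis was 4.5 to 5.4%. For HOT the standard-error ratio was 0.97 to 1.01 and the power gain 0 to 5 points.

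**The case against.** The strongest reply is that an unadjusted comparison after matching on a score that contains GA and BW is valid. That stands. A reader might infer from the GA gaps within pairs that every matched comparison is confounded by GA. The plan does not support that: the score contains both variables, within-pair gaps do not imply a group difference, and Step 2 shows a mean difference near zero with no inflated type I error.

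A reader might also count covariates with a standardised mean difference (SMD) beyond 0.1. In the second simulation about 9.3 of 15 (30 pairs) and 4.7 of 15 (86 pairs) exceeded it. This is not failed matching. Under simple randomisation the SMD has SD of about √(2/n), so P(|SMD| > 0.1) is 0.70 at n = 30 and 0.51 at n = 86, or about 10.5 and 7.7 of 15. The matched sets were better balanced than that.

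Three further objections stand in part:

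- It would be wrong to say the plan has no covariate adjustment, since mortality has a regression. Yet forward selection may drop GA or BW from it, and it may not use the matched set.
- The power comparisons are with t-tests. If stay and oxygen days are skewed, the planned test is Wilcoxon-Mann-Whitney, which was not simulated, so the gains are not exact gains over the plan.
- The precision gain falls mainly on two secondary outcomes and is small when R² is low.

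None of this removes the gap: no balance diagnostic is described, and a cheap gain in precision is left unused.

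**Conclusion.** The point holds as a shortfall in precision and in safeguards, not as a demonstrated bias. BPD severity, HOT and all secondary outcomes rest on unadjusted independent-group tests after matching, with no stated check that matching worked. Imbalance in GA or BW is a risk, from chance or from a misspecified score, and it grows as the number of pairs falls.

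The size cannot be fixed from the documents. The ranges of about 1 to 26 power points (about 25 pairs) and 2 to 7 points (about 73 pairs) assume a 0.5 SD effect, R² between 0.1 and 0.5, a correctly specified score and an approximately normal outcome. They include some gain from replacing a conservative test. The 0 to 5 points for HOT come from the second set of assumptions, and no figure is available for BPD severity. For the primary outcomes severity and HOT, the main benefit is therefore protection against imbalance rather than power.

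**What to change.** Add to the Statistical Analysis section:

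1. In the matched set, analyse BPD severity, HOT and each secondary outcome by regression on imaging with GA and BW as pre-specified covariates and standard errors clustered on pair. Use log days for hospital stay and oxygen duration, and state explicitly how deaths before discharge are handled. Use logistic models for binary outcomes and ordinal models for graded ones.
2. Report each effect with a 95% confidence interval.
3. Tabulate SMDs for all 15 covariates after matching, as a diagnostic. Do not add covariates automatically at |SMD| > 0.1: with about 30 pairs that could mean some nine data-chosen terms in 60 infants, an analysis whose error rates were not examined here.
4. State whether the mortality regression uses the matched set or the full cohort.

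The cost is a few sentences and some re-analysis of data already held. The small downside is a modelling assumption about how GA and BW relate to each outcome.

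### Sex and 5-min Apgar score are collected and precede any chest image, yet neither is in the propensity score or the mortality regression

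*Combined protocol and SAP*

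**What the plan says.** The unheaded paragraph on data collection names the baseline variables. Sex appears under "demographics [i.e., sex, gestational age, age at admission, birth weight (BW", and the Apgar score closes the perinatal group: "sepsis, PDA, 5-min Apgar score".

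The Statistical Analysis section applies matching to "the associations between typical chest imaging findings and the primary and secondary outcomes, a propensity score analysis with 1:1 matching was performed". Its list opens "The following covariates were included based on previous studies: GA, BW, cesarean section, CAM, PIH, sepsis, RDS, PDA" and continues with prenatal and postnatal glucocorticoids, NEC, IVH, an entry written RSD, invasive ventilation of at least 7 days, and two or more red cell transfusions. Matching is nearest-neighbour with a caliper of 0.01 SD of the logit. The mortality model then takes the imaging finding and "the above 15 covariates", with forward likelihood-ratio selection.

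Two imaging times are mentioned. Eligibility requires "chest imaging examination (CXR or CT) in the first week after birth", and the background refers to "the presence of bubbles/cystic appearance on CXR after 28 days of life". The primary outcomes are given as: "Primary outcomes were the severity of BPD, HOT at discharge, and mortality between 28 days after birth and 2 years of age".

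**The concern.** A propensity match balances, on average, what is in the score. It gives no assurance about variables left out, except so far as they are correlated with those included. If sex or condition at birth is related both to the imaging finding and to an outcome, given the listed covariates, part of the matched difference would belong to that variable rather than to imaging. All primary and secondary outcomes are exposed, because all of them pass through the same match. The mortality regression offers no second chance: it cannot select a variable that is not among its candidates.

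The usual reason for caution in adding a covariate is that it may lie on the path from exposure to outcome. That does not apply here. Sex is fixed before birth and the score is taken at five minutes, so both come before an image in the first week or after 28 days. The plan does not state this ordering; it follows from what the variables are.

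The omission also stands out against the plan's own pattern. Eight perinatal factors are collected, seven are on the list, and the Apgar score is the exception. Gestational age and birth weight are on the list and sex is not.

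**Working it through.** **1. The plan's own count.** Eight entries (GA, BW, cesarean section, CAM, PIH, sepsis, RDS, PDA) plus seven (prenatal glucocorticoid, postnatal glucocorticoid, NEC, IVH, RSD, IMV, PRBC) = 15. This reproduces the stated figure, so the two variables were not lost when the text was extracted.

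**2. Collected against listed.** Collected before the outcomes: 4 demographics + 8 perinatal factors + 5 items of management + 3 complications = 20. Of these, 14 are on the list (the fifteenth entry, RSD, is not among the collected variables). The other 20 − 14 = 6 are sex, age at admission, 5-min Apgar, surfactant, noninvasive ventilation and ROP. Only sex and Apgar are certain to precede any image. Age at admission could follow an early one, and the other three are events or treatments after birth.

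**3. Size, as an illustration only.** The documents give no distribution of sex or Apgar by imaging group, so every input here is assumed. For one omitted binary factor with prevalence p1 and p0 in the matched groups and outcome risk ratio RR:

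bias factor = (1 + p1(RR − 1)) / (1 + p0(RR − 1))

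standardized difference = (p1 − p0) / √[(p1(1 − p1) + p0(1 − p0)) / 2]

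| Assumed imbalance | Odds ratio | Std. difference | RR 1.2 | RR 1.5 | RR 2 | RR 3 |
|---|---|---|---|---|---|---|
| Male 60% v 50% | 1.5 | 0.20 | 1.02 | 1.04 | 1.07 | 1.10 |
| Low Apgar 21% v 15% | 1.5 | 0.16 | 1.01 | 1.03 | 1.05 | 1.09 |
| Low Apgar 25% v 15% | 1.9 | 0.25 | 1.02 | 1.05 | 1.09 | 1.15 |

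Example, second row at RR 3: (1 + 0.21 × 2) / (1 + 0.15 × 2) = 1.42 / 1.30 = 1.09. If the groups are balanced on the factor, the bias factor is 1.00.

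**4. Does the match leave such gaps, and what does closing them cost?** A simulation of 600 cohorts per setting assumed 200, 400 or 800 infants, 30% with the finding, 50% male, 15% with low Apgar, and 14 other independent covariates (2 continuous with log-odds −0.4 and −0.3; 12 binary at 30% with log-odds 0.35 each). It used a logistic propensity score and greedy 1:1 matching without replacement at the plan's 0.01 SD caliper.

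- With no relation to imaging, leaving the two out caused no average imbalance.
- With an odds ratio of 1.5 for sex, the mean standardized difference on sex after matching was 0.19 to 0.22 without the terms.
- For low Apgar it was 0.14 to 0.15 (odds ratio 1.5) or 0.25 to 0.26 (odds ratio 2).
- With both terms in the score, all were within 0.02 of zero.

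Mean matched pairs, without → with the two terms:

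| Odds ratios (sex, Apgar) | 200 infants | 400 infants | 800 infants |
|---|---|---|---|
| 1, 1 | 25.3 → 24.8 | 72.7 → 72.5 | 182.6 → 181.6 |
| 1.5, 1.5 | 25.4 → 24.7 | 73.1 → 72.1 | 183.1 → 180.6 |
| 1.5, 2 | 25.5 → 24.7 | 73.4 → 71.3 | 184.6 → 180.6 |

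The smallest loss is (72.7 − 72.5)/72.7 = 0.3% and the largest (25.5 − 24.7)/25.5 = 3.1%.

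**The case against.** Choosing covariates from earlier literature is a legitimate method, and the plan says that is what it did. Those sources are not available here, so they may have considered these two variables and set them aside. Six collected variables are off the list, so the plan evidently did not mean to match on everything. This stands as a reason not to call the omission an error. It does not explain why two baseline values already held were left out while treatments given later in the stay were included.

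The illustration is also open to attack, and much of that stands. Treating the other covariates as independent gives them no information about condition at birth; correlation with gestational age or RDS would tend to shrink the Apgar gap. Dichotomizing the score is an assumption, since the plan does not say how it would be coded. The upper ends need an outcome risk ratio of 3. A risk-ratio factor says nothing direct about hospital stay or duration of oxygen.

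On balance, the section does specify two-group tests that could be applied to sex and Apgar. It does not say they are repeated after matching and names no explicit balance check, so whether a residual difference would be seen is unclear rather than excluded.

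A reader might infer that the matched results are biased by sex or condition at birth. The documents do not support that: they contain nothing on how either variable relates to imaging or outcome. A reader might also take the RSD entry as a hidden reference to one of the two, or as further evidence of a faulty model. Nothing in the text supports either reading; it is a clerical matter and adds no weight.

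**Conclusion.** The point holds as a gap in adjustment. Both variables are collected, both precede imaging, both are missing from the score and from the regression that reuses its list, and no specific reason is given. That much is certain from the text.

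The consequence is not. Bias arises only if sex or Apgar is associated with both the imaging finding and the outcome after the listed covariates are matched, and neither its size nor its direction can be derived from the documents. On the assumptions shown, the factor on a risk ratio runs from 1.00 (groups balanced) to 1.10 for sex, to 1.09 for low Apgar at an odds ratio of 1.5, and to 1.15 only for a 10-point low-Apgar gap, which needs an odds ratio near 2. These would be modest shifts. The change should be made because it is cheap and shows whether there is a problem, not because a distortion has been demonstrated.

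**What to change.** - **Match.** Add sex and 5-min Apgar score to the propensity model, state the form in which Apgar enters, and rerun the match. Report the number of pairs, standardized differences for all covariates including these two, and the primary and secondary outcome comparisons with and without the two terms. The document is written in the past tense; if the match on the listed covariates has already been run, label the re-specified match a sensitivity analysis. If the two are still left out, say why and report their balance after matching.
- **Mortality.** Fit a model with imaging, sex and Apgar forced in. Adding them only as candidates is not enough, because forward selection could drop either one, or the imaging term itself. Label it a sensitivity analysis if deaths are few.
- **Clerical.** Define RSD or delete it. The propensity list then has 15 + 2 = 17 entries if RSD is a distinct variable, or 14 + 2 = 16 if it is deleted.

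**Cost.** New SAP wording and a rerun on data already collected. Some pairs may be lost under the narrow caliper (0.3% to 3.1% in the illustration). Infants without an Apgar score could drop out or fall under the exclusion for inadequate clinical data. The enlarged mortality model may be unstable with few deaths. The lost pairs and lost records should both be reported.
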